4.3. Prohibitions and Restrictions

Potential subjects must be willing and able to adhere to the following prohibitions and restrictions during the course of the study to be eligible for participation:

1. If a woman of childbearing potential is heterosexually active, she must remain on a highly effective method of birth control (see inclusion criteria 6) during the study and for 12 weeks after receiving the last dose of any study agent.

2. If a man who has not had a vasectomy and is sexually active with a woman of childbearing potential must use a barrier method of birth control, eg, either condom with spermicidal foam/gel/film/cream/suppository or partner with occlusive cap (diaphragm or cervical/vault caps) with spermicidal foam/gel/film/cream/suppository, and all men must also not donate sperm during the study and for 12 weeks after receiving the last dose of study drug.
3. Must agree not to receive a live virus or bacterial vaccination during the study or up to 12 weeks after the last administration of any study agent.
4. Must agree not to receive a BCG vaccination during the study or up to 52 weeks after the last administration of any study agent.
5. Must comply with restrictions on prestudy and concomitant medications (see Section 8).
6. Must avoid prolonged sun exposure and avoid use of tanning booths or other UV light sources to the palms and soles during study.
7. Must agree that every effort should be made to stop smoking.
8. Must agree not to participate in other clinical study which will collect the skin biopsy samples during the study and for 12 weeks after receiving the last dose of any study agent.

5. TREATMENT ALLOCATION AND BLINDING

Treatment Allocation

Procedures for Randomization

Central randomization will be implemented in this study.

At week 0, subjects will be randomly assigned to 1 of 3 treatment groups in a 1:1:1 ratio based on a computer-generated randomization schedule prepared before the study by or under the supervision of the sponsor. The randomization will be balanced by using randomly permuted block and will be stratified by PPPASI total score range at baseline (≤ 20 score, 21-30 score, ≥ 31 score) and smoking status (smoking or non-smoking). The interactive web response system (IWRS) will assign a unique treatment code, which will dictate the treatment assignment and matching study drug kit for the subject. The requestor must use his or her own user identification and personal identification number when contacting the IWRS, and will then give the relevant subject details to uniquely identify the subject.

At week 16, Group III subjects will be allocated in a 1:1 ratio to 1 of 2 active treatment groups. Stratification factors will be PPPASI total score range at baseline (≤ 20 score, 21-30 score, ≥ 31 score) and smoking status (smoking or non-smoking).

Blinding

The study site personnel, investigators, and the randomized subjects will be blinded to the subject's allocation.

The investigators and subjects will be unblinded after the last subject has completed the Week 60 visit. The end of the study is defined as the time when the last subject completes the Week 84 visit. Database locks will occur at Weeks 16, 24, 52 and 84. Additional DBLs may also occur at other times during the study.

In general, randomization codes will be disclosed fully only after the last subject has completed the Week 60 visit. However, in order to conduct the safety monitoring and interim analysis, the randomization codes and the translation of randomization codes into treatment and control groups will be disclosed to IDMC and Statistical Support Group (SSG) who support IDMC and only for those subjects included in the safety/interim analysis.

Emergency Unblinding

The investigator will not be provided with randomization codes. The codes will be maintained within the IWRS, which has the functionality to allow the investigator to break the blind for an individual subject.

Data that may potentially unblind the treatment assignment (ie, study drug serum concentrations, antibodies to study drug, study drug preparation/accountability data, treatment allocation, biomarker and specific laboratory data) will be handled with special care to ensure that the integrity of the blind is maintained and the potential for bias is minimized. This can include making special provisions, such as segregating the data in question from view by the investigators, clinical team, or others as appropriate until the time of database lock and unblinding.

Under normal circumstances, the blind should not be broken until the last subject has completed the Week 60 visit. Otherwise, the blind should be broken only if specific emergency treatment/course of action would be dictated by knowing the treatment status of the subject. In such cases, the investigator may in an emergency determine the identity of the treatment by contacting the IWRS. It is recommended that the investigator contact the sponsor or its designee if possible to discuss the particular situation, before breaking the blind. Telephone contact with the sponsor or its designee will be available 24 hours per day, 7 days per week. In the event the blind is broken, the sponsor must be informed as soon as possible. The date, time, and reason for the unblinding must be documented by the IWRS, in the appropriate section of the electronic case report form (eCRF), and in the source document. The documentation received from the IWRS indicating the code break must be retained with the subject's source documents in a secure manner.

Subjects who have had their treatment assignment unblinded should continue to return for scheduled evaluations. The decision to continue or discontinue study treatment for these subjects will be based upon consultation of the investigator with the medical monitor. Additionally, a

given subject's treatment assignment may be unblinded to the sponsor, Independent Ethics Committee (IEC)/Institutional Review Board (IRB) and site personnel to fulfill regulatory reporting requirements for serious unexpected associated adverse reactions (SUAs). A separate code break procedure will be available for use by Sponsor's Global Medical Safety (GMS) group to allow for unblinding of individual subjects to company with specific requests from regulatory or health authorities.

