The primary hypothesis is that CNTO1959 treatment is superior to placebo as assessed by the change from the baseline of Palmoplantar Pustulosis Area and Severity Index (PPPASI) total score at Week 16.

OVERVIEW OF STUDY DESIGN

This is a Phase 3, randomized, double-blind, multicenter placebo-controlled study in subjects with palmoplantar pustulosis. This study will be conducted using an adaptive statistical design permitting one interim analysis and the potential to stop the study for futility and increase sample size for the final analysis with a maximum allowable sample size of 225 patients.

Week 0 through Week 60 (Blinded Treatment Period)

Approximately 150-225 subjects who satisfy all inclusion and exclusion criteria will be randomized in a 1:1:1 ratio to one of three arms:

- **Group I** (n = 50, max75): CNTO 1959 200 mg at Weeks 0, 4, 12 and q8w thereafter through Week 60.
- **Group II** (n = 50, max75): CNTO 1959 100 mg at Weeks 0, 4, 12 and q8w thereafter through Week 60.
- **Group III** (n = 50, max75): Placebo at Weeks 0, 4, and 12. Beginning at Week 16, subjects will be randomized in a 1:1 ratio to CNTO 1959 200 mg arm (Group IIIa) or 100 mg arm (Group IIIb), and will receive the assigned dose of CNTO 1959 at Weeks 16, 20 and q8w thereafter through Week 60.

Subject will be assigned to 1 of 3 treatment groups using a stratified block randomization method in a 1:1:1 ratio at Week 0 and Group III subjects will be allocated in a 1:1 ratio to 1 of 2 active treatment groups at Week 16. Stratification factors will be PPPASI total score range at baseline (≤ 20 score, 21-30 score, ≥ 31 score) and smoking status (smoking or non-smoking).

After Week 60 until Week 84 (Observational Period)

The observational period will begin from Week 60 and extend until Week 84. All subjects will no longer receive the study drug during the observational period. Efficacy and safety will be evaluated at Week 72, and the durability of clinical response and safety at Week 84.

The investigators and subjects will be unblinded after the last subject has completed the Week 60 visit. The end of the study is defined as the time when the last subject completes the Week 84 visit. Database locks (DBLs) will occur at Weeks 16, 24, 52 and 84. Additional DBLs may also occur after Week 52 DBL during the study.

An Independent Data Monitoring Committee (IDMC) will be constituted for safety monitoring and interim analysis review of this study.

SUBJECT POPULATION

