3. STUDY DESIGN AND RATIONALE

3.1. Overview of Study Design

This is a Phase 3, randomized, double-blind, multicenter placebo-controlled study in subjects with palmoplantar pustulosis. The target population is adult men or women, with a diagnosis of palmoplantar pustulosis (with or without PAO) for at least 24 weeks before screening. Subjects must have a PPPASI total score ≥ 12 and a PPPASI severity score of pustules/vesicle on the

palms or soles ≥ 2 at screening and baseline. Subjects must have inadequate response to conventional therapies (topical treatment, and/or phototherapy, and/or systemic treatment).

Subjects with drug-induced palmoplantar pustulosis (eg, a new onset of palmoplantar pustulosis or an exacerbation of palmoplantar pustulosis from beta blockers, calcium channel blockers, or lithium, or biologic therapy etc.) are excluded. Subjects who have ever received CNTO 1959 are also excluded.

This study will be conducted using an adaptive statistical design permitting one interim analysis and the potential to stop the study for futility and increase sample size for the final analysis with a maximum allowable sample size of 225 patients.

Key features of study drug administration for each treatment group are outlined below; for details regarding concomitant placebo administrations to maintain the blind, please see Section 6, Dosage and Administration.

Week 0 through Week 60 (Blinded Treatment Period)

As depicted in [Figure 1](#), approximately 150-225 subjects who satisfy all inclusion and exclusion criteria will be randomized in a 1:1:1 ratio to one of three arms:

- **Group I** (n = 50, max75): CNTO 1959 200 mg at Weeks 0, 4, 12 and q8w thereafter through Week 60.
- **Group II** (n = 50, max75): CNTO 1959 100 mg at Weeks 0, 4, 12 and q8w thereafter through Week 60.
- **Group III** (n = 50, max75): Placebo at Weeks 0, 4, and 12. Beginning at Week 16, subjects will be randomized in a 1:1 ratio to CNTO1959 200 mg arm (Group IIIa) or 100 mg arm (Group IIIb), and will receive the assigned dose of CNTO 1959 at Weeks 16, 20 and q8w thereafter through Week 60.

Subject will be assigned to 1 of 3 treatment groups using a stratified block randomization method in a 1:1:1 ratio at Week 0 and Group III subjects will be allocated in a 1:1 ratio to 1 of 2 treatment groups at Week 16. Stratification factors will be PPPASI total score range (≤ 20 score, 21-30 score, ≥ 31 score) and smoking status (smoking or non-smoking).

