11.3.3. Primary Analysis

Primary endpoint of this study is change from baseline in PPPASI total score at Week 16. In the primary efficacy analyses, data from all randomized subjects will be analyzed according to their assigned treatment group. In this primary analysis, the change from baseline in PPPASI total score through Week 16 will be analyzed using an MMRM with treatment (CNTO 1959 high dose, CNTO 1959 low dose, or placebo), smoking status (smoking or non-smoking), week (2, 4, 8, 12, 16), and treatment-by-week interaction as fixed effects and baseline PPPASI score as a covariate. Un-imputed data will be used for MMRM analyses and data is assumed to be missing at random (MAR). An unstructured covariance structure will be used to model the within-patient error. If the model with unstructured covariance structure doesn't converge, the compound symmetry structure will be used. Based on the MMRM model described above, treatment effects of CNTO 1959 groups versus placebo group at Week 16 will be estimated based on least-square (LS) means of the differences. The p-values for the LS mean differences along with the 2-sided 95% CIs will be presented.

Sensitivity analyses for primary endpoint (change from baseline in PPPASI total score at Week 16) will be performed using an ANCOVA model with treatment (CNTO 1959 high dose, CNTO 1959 low dose, or placebo) and smoking status (smoking or non-smoking) as factors and baseline PPPASI score as a covariate, based on the data with and without imputation of last observation carry forward (LOCF). The last available post-baseline PPPASI total score will be carried forward to impute the PPPASI total score that are missing after discontinuation of treatment up to Week 16 of the double-blind treatment period.

Furthermore, subgroup analyses will be performed to evaluate consistency of the primary endpoints over demographics and baseline disease characteristics as appropriate. The exploratory analyses for the primary endpoints to evaluate the dose-response may be performed if deemed appropriate. Additional efficacy analyses may also be performed and will be documented in the SAP.

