11.3.4. Major Secondary Analyses

Major secondary endpoints of this study are not prospectively powered and all p-values reported for secondary endpoints will not adjust for multiple comparisons. Major secondary analyses are:

- The change from baseline in PPSI through Week 16 will be analyzed using the same MMRM model as described for the primary analysis, except for including the baseline PPSI score, instead of baseline PPPASI score, as the covariate. Treatment effects of CNTO 1959 groups versus placebo group will be estimated based on least-square (LS) means of the differences. The p-values for the LS mean differences along with the 2-sided 95% CIs will be presented. The change from baseline in PPSI through Week 16 will also be summarized by treatment group and week using descriptive statistics.
- The proportion of subjects who achieve a PPPASI-50 at Week 16 will be compared between the CNTO 1959 treatment groups and placebo group using a CMH chi-square test stratified by baseline PPPASI total score (≤ 20 , 21-30, ≥ 31) and smoking status (smoking or non-smoking). The proportion through Week 16 will also be summarized by treatment group and week using frequencies and percentages with 95% CI.

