11.3.5. Other Efficacy Analyses

For other secondary endpoints (including exploratory endpoints), the continuous variables will be summarized by treatment group and week using descriptive statistics, which will include the number of subjects (N), mean, SD, median, minimum, and maximum and the measurements through Week 16 will be analyzed using an MMRM model where there are repeated measurements; or an analysis of variance model based on appropriate rank scores or ANCOVA model where there is no repeated measurement. The categorical variables will be summarized by treatment group and week using frequencies and percentages. The binary variables through Week 16 will be compared using stratified CMH chi-square test or Fisher's exact test.

Other secondary endpoints are as follows:

- Change from baseline in PPPASI total score over time
- Change from baseline in PPSI total score over time
- Proportion of subjects who achieve a PPPASI-50 over time
- Proportion of subjects who achieve a PPPASI-75, PPPASI-90, PPPASI-100 over time
- Proportion of subjects who achieve a PPSI-50, PPSI-75, PPSI-90, PPSI-100 over time
- Change from baseline in PGA score over time
- Proportion of subjects who achieve a PGA score of cleared (0) or minimal (1) over time
- Proportion of subjects who achieve a PGA score of cleared (0) or minimal (1) and have at least a 2-grade improvement from baseline over time
- Change from baseline in DLQI score over time
- Change from baseline in SF-36 score over time
- Change from baseline in EQ-5D score over time

Exploratory endpoints are as follows:

- Change from baseline in EQ-5D score in PAO subjects over time

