Attachment 1: PPPASI (Palmo-Plantar Pustular Area and Severity Index)

The PPPASI is a system used for assessing and grading the severity and area of palmoplantar pustulosis lesions and their response to therapy. The PPPASI produces a numeric score that can range from 0 to 72. The severity of the disease is calculated as follows.

In the PPPASI system, the palms and soles are divided into 4 regions: the right palm, left palm, right sole, and left sole, which account for 20%, 20%, 30%, and 30% of the total body BSA of the palms and soles, respectively. Each of these areas is assessed separately for erythema, pustules and desquamation, which are each rated on a scale of 0 to 4.

The scoring system for the signs of the disease (erythema, pustules/vesicle and desquamation /scale) is: 0 = none, 1 = slight, 2 = moderate, 3 = severe, and 4 = very severe.

The scale for estimating the area of involvement for pustular lesions is outlined below.

- 0 = no involvement
- 1 = 1% to 9% involvement
- 2 = 10% to 29% involvement
- 3 = 30% to 49% involvement
- 4 = 50% to 69% involvement
- 5 = 70% to 89% involvement
- 6 = 90% to 100% involvement

The PPPASI formula is:

$$\text{PPPASI} = (E + P + D) \text{ Area} \times 0.2 \text{ (right palm)} + (E + P + D) \text{ Area} \times 0.2 \text{ (left palm)} + (E + P + D) \text{ Area} \times 0.3 \text{ (right sole)} + (E + P + D) \text{ Area} \times 0.3 \text{ (left sole)}$$

Where E = erythema, P = pustular/vesicle and D = desquamation/scale

References

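### Do baseline PPPASI scores of 20.1-20.9 and 30.1-30.9 fall outside the randomization strata in a way that calls for a change?

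*Protocol*

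**What the plan says.** Section 5 (Treatment Allocation and Blinding) says that the Week 0 randomization will be "stratified by PPPASI total score range at baseline (≤ 20 score, 21-30 score, ≥ 31 score" and by smoking status. For the Week 16 allocation of Group III it repeats: "Stratification factors will be PPPASI total score range at baseline (≤ 20 score, 21-30 score, ≥ 31 score) and smoking status (smoking or non-smoking". Section 3.1 gives the same three bands after "Stratification factors will be PPPASI total score range", and so does the study design overview in the Synopsis.

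Section 11.3.4 (and the Synopsis) compares PPPASI-50 at Week 16 by a "CMH chi-square test stratified by baseline PPPASI total score", again with these bands, and smoking status. Section 11.3.5 adds: "The binary variables through Week 16 will be compared using stratified CMH chi-square test" or Fisher's exact test, without naming the strata.

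The score is defined in Attachment 1. Erythema, pustules/vesicle and desquamation are each scored 0 to 4 per region and area 0 to 6, and the four regions "account for 20%, 20%, 30%, and 30% of the total body BSA" of the palms and soles. The total is the weighted sum of the four regional products, with a stated range of 0 to 72.

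The primary model in section 11.3.3 has "treatment-by-week interaction as fixed effects and baseline PPPASI score as a covariate". The protocol does not say how a decimal score is assigned to a band.

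**The concern.** The bands ≤20, 21-30 and ≥31 cover every case only if the total is a whole number. With weights of 0.2 and 0.3 it is not. Read literally, a subject scoring 20.4 or 30.4 belongs to no stratum at either randomization and to none in the stratified test of a major secondary endpoint.

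The practical worry is different. Three readings are natural: round to the nearest whole number, truncate, or cut strictly above 20 and above 30. They disagree for some gap scores. If the randomization system used one and the analysis program another, some subjects would be analysed in a stratum other than the one they were randomized in. The PPPASI-50 p-value would then depend on an unwritten choice.

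**Working it through.** **Inputs.** Attachment 1: sign scores 0-4, area 0-6, weights 0.2, 0.2, 0.3, 0.3. Section 4.1: total ≥12 and a pustules/vesicle score ≥2. Sections 5 and 11.3.4: the three bands. The protocol gives no baseline PPPASI distribution, so any count of affected subjects is an assumption.

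**1. The protocol's own range.** The largest regional product is (4+4+4) × 6 = 72, and 72 × (0.2+0.2+0.3+0.3) = 72. This reproduces the stated maximum.

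**2. The grid.** With integer regional products a, b (palms) and c, d (soles), total = 0.2(a+b) + 0.3(c+d) = 0.1 × [2(a+b) + 3(c+d)]. Totals are therefore multiples of 0.1. Listing every total that an eligible subject can have gives all nine values 20.1-20.9 and all nine values 30.1-30.9. Examples:

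- Palms 5 × 3 = 15 each, soles 6 × 4 = 24 each: 0.2 × 30 + 0.3 × 48 = 6.0 + 14.4 = 20.4.
- Palms 7 × 4 = 28 each, soles 8 × 4 = 32 each: 0.2 × 56 + 0.3 × 64 = 11.2 + 19.2 = 30.4.
- Palm products 12 and 14, sole products 21 and 30: 0.2 × 26 + 0.3 × 51 = 5.2 + 15.3 = 20.5.

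The gaps are real. If left and right are identical, only the even tenths occur.

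**3. How many subjects (assumed distributions).** For a normal baseline truncated at 12 with mean 24-28 and SD 8-11, 6.2-7.8% fall in a gap. Widening to mean 20-30 and SD 8-12 gives 5.5-7.8%. In counts, 0.055 × 150 ≈ 8 to 0.078 × 150 ≈ 12 subjects; of 225, about 12 to 18; of the 100 in one dose-versus-placebo comparison, about 6 to 8.

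Not all of these would change stratum between two rules. Under the narrower assumptions:

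- Rounding and truncation differ only at 20.5-20.9 and 30.5-30.9: 3.5-4.3% of subjects.
- Rounding and strict cut-points differ only at 20.1-20.4 and 30.1-30.4: 2.8-3.5%.
- Truncation and strict cut-points differ at all 18 values: 6.2-7.8%.

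**4. Effect on the PPPASI-50 test.** Simulation with 50 per arm, baseline normal with mean 26 and SD 9.5 truncated at 12, 60% smokers, randomization balanced on rounded strata, placebo response about 30%, 6,000 runs:

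| Strata used in the test | Type I error | Power at odds ratio 3 |
|---|---|---|
| Strict >20, >30 | 4.95% | 75.0% |
| Truncated | 4.75% | 75.0% |
| Rounded | 4.88% | 75.3% |

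The Monte Carlo standard error of one rate is √(0.05 × 0.95/6000) = 0.28 percentage points under the null and √(0.75 × 0.25/6000) = 0.56 points for power. The rules were applied to the same simulated trials, and the significance call differed in about 1% of runs under the null and 3% at odds ratio 3. The standard error of a paired difference is therefore about √(0.01/6000) = 0.13 and √(0.03/6000) = 0.22 points. The largest differences in the table, 0.20 and 0.3 points, are about 1.5 and 1.4 of these standard errors. A second simulation gave 4.8-4.9% and 75.8-76.2% across the three rules.

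**5. Which analyses use the bands.** The primary MMRM and the ANCOVA sensitivity analyses adjust for the baseline score as a continuous covariate and for smoking status, so the bands do not enter them. Section 11.3.1 includes all randomized subjects in the efficacy analyses and bases most secondary summaries on subjects with evaluable measurements. A decimal baseline score does not make a measurement unevaluable, so nothing there removes a gap subject from the PPPASI-50 test.

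**The case for a change.** The strongest case for a change is that this is more than a detail left to the SAP. The protocol itself fixes the cut-points, for randomization as well as analysis, and they do not fit its own score. Randomization is not governed by the SAP. Under any plausible baseline distribution some gap subjects are to be expected. Contiguous ranges would cost little and would make the randomized and analysed strata plainly identical.

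The textual part of this stands. The consequence does not. Section 5 routes allocation through a central interactive system, which cannot allocate a subject without a stratum, so its specification must already contain a mapping. The Week 16 allocation uses the baseline score again, so the stratum assigned at Week 0 carries over. Section 11 leaves specific details of the analysis to the SAP, and taking the stratum from the randomization record is an ordinary choice there. Nothing in the protocol sets up two different rules; a mismatch would be a guess about documents not shown.

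One remnant is fair: with two rules available, an individual trial's PPPASI-50 result could cross the significance line in about 1-3% of simulated cases. Settling one rule before unblinding closes that, and this is routine analysis specification. Section 11.3.4 also says the major secondary endpoints are not prospectively powered and their p-values are not adjusted for multiplicity, so no confirmatory claim rests on this test.

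**Conclusion.** The labels are imprecise: 18 attainable scores lie between the written bands and the protocol states no mapping. No change to the plan follows. The primary analysis and its ANCOVA sensitivity analyses do not use the bands, and a mapping applied to a pre-dose score cannot favour a treatment group. The stratified PPPASI-50 test performs the same under each of the three sensible mappings, with Type I error within 0.20 percentage points and power within 0.3 points. Contiguous ranges would only write down a rule that the randomization system must already apply.

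The share of subjects in the gaps (5.5-7.8%) and the simulation results rest on assumed baseline distributions, smoking prevalence and response rates. The absence of bias and the irrelevance to the primary test do not depend on those assumptions. The conclusion for the PPPASI-50 test supposes that one mapping is fixed before unblinding.
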